Fecal samples from all children will be collected repeatedly for microbiome analyses. The protocol is described in Deliverable 2.1.

2.3.4.3. *Outcomes*

To evaluate the effectiveness of the intensive personalized dietary intervention changes in dietary, lifestyle, growth-related and metabolic factors will be assessed, as described below and in Deliverable 2.8.

Dietary factors

Changes in dietary factors are expected after the personalized intervention. In specific, energy intake, the composition of the diet in macro-nutrients, especially of saturated and trans-fatty acid intake [31] as well as specific micro-nutrients, such as vitamin D and iron [32, 33] are expected to improve. What is more, consumption of specific food groups, such as fruits and vegetables [34-37] and dairy products [37-40] is expected to change. Finally, adherence to the Mediterranean Diet is expected to increase [41].

Other lifestyle factors

Levels of children's physical activity after the implementation of the platform-derived personalised diet are expected to increase [42-44].

Growth related factors

Regarding children's weight, height and BMI status is expected to change and will be compared to the available growth charts proposed by the World Health Organization [45].

Clinical outcomes

To test the effect of the personalised diet intervention on clinical diabetes we will evaluate possible improvement in the metabolic profile of children such as blood glucose, insulin, A1C, HOMA-IR (Type II diabetes) and c-peptide (Type I diabetes) [46, 47]. In addition, cardiometabolic risk factors such as total cholesterol, LDL cholesterol, HDL cholesterol, LDL/HDL cholesterol ratio and triglycerides will be also assessed [48].

Microbiome-related factors

In the post intervention phase, changes in the gut microbiome related to dietary modifications are expected to occur [49]. We also expect to detect alteration of the metabolome profile at the systemic level (blood and urine), such as changes in the quantity of colonic short chain fatty acid [50].

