2.3.5. Sample

2.3.5.1. Sample size

For **Study I phase I**, the working sample will be 200 children, 8-18 years old. By this sample size a statistical power of 92% will be achieved to evaluate two-sided correlation coefficients between the investigated measurements at the level of r = 0.33 [* power one correlation 0 .30, n(200)].

For **Study I phase II**, the required sample will be 80 children (40 per Group A or B) aged 8-18 years old, in order to achieve statistical power of at least 90% at 5% significance level of two-sided hypotheses for the evaluation of 0.75 standard deviations (SD) mean differences in the primary endpoint of the Study [power two means 100, diff (15) sd (20) n (80)].

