2.3.6. Statistical analysis

Descriptive statistics will be used to present the characteristics of the participating children. Linear regression analyses will be performed with weight and BMI, as well as blood glucose, insulin, A1C, HOMA-IR as dependent variables and physical activity levels, children's and mother's smoking habits, nutritional status including energy intake, consumption of specific food groups and KIDMED score, medical history, genotype and metabolome as the independent variables.

Between Group comparisons for the baseline measurements of the phase II of Study I, will be performed using t-test or Mann-Whitney test, to ensure comparability of the Groups. Then, children

enrolled in the intervention diet will (Group A) be compared to those of the control diet (Group B), regarding their weight and BMI status as well as regarding the glycemic control as indicated by blood glucose, insulin, A1C, HOMA-IR (i.e., primary end points), using Repeated Measures Analysis of Variance (RMANOVA). Moreover, the 2Groups will be compared regarding various cardiometabolic risk factors such as total cholesterol, LDL cholesterol, HDL cholesterol, LDL/HDL cholesterol ratio and triglycerides, improvement in nutritional status including energy intake and consumption of specific food groups, as well as urine biomarkers, biomarkers of intestinal inflammation and microbiome profile, using the aforementioned method. All necessary adjustments (based on the baseline analyses) will be performed to ensure the robustness of the results.

The analyses will be performed by using STATA v15 software (STATA Corp LLL, College Station, TX, USA).

Finally, additional statistical analysis with the view of deriving additional insights and influences in personalised nutrition will be presented in D2.5.

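### Study I Phase II is sized for one unnamed primary endpoint, but its analysis names six (or four), so the stated 5% error rate and 90% power cannot both describe the primary analysis as listed

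*Protocol*

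**What the plan says.** Section 2.3.5.1 (Sample size) plans Phase II for "0.75 standard deviations (SD) mean differences in the primary endpoint of the Study", with power of "at least 90% at 5% significance level of two-sided hypotheses". The endpoint is in the singular and is not named. The software call is "power two means 100, diff (15) sd (20) n (80", with no unit that would show which variable has a difference of 15 and an SD of 20. On size, "the required sample will be 80 children (40 per Group A or B").

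Section 2.3.6 (Statistical analysis) compares Group A with Group B by repeated-measures ANOVA on "weight and BMI status as well as regarding the glycemic control as indicated by blood glucose, insulin, A1C, HOMA-IR (i.e., primary end points"). Read naturally, that makes six primary end points: weight, BMI, blood glucose, insulin, A1C and HOMA-IR. If the bracket belongs only to glycemic control, it makes four. The section gives no significance level for these comparisons and does not say which of them the sizing refers to. Its one sentence on adjustment is "All necessary adjustments (based on the baseline analyses) will be performed to ensure the robustness of the results", which is tied to the baseline comparisons.

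Section 2.3.4.3 (Outcomes) marks no outcome as primary. The CONSORT table in section 2.6 (item 6a) nevertheless points to pages 16-19 for fully defined primary and secondary outcomes.

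**The concern.** The number of children and the set of primary end points are both fixed in this protocol, and they disagree. A design with one primary endpoint at 5% and 90% power is a different design from one with six. With several, the error rate and the power depend on whether one, some or all must succeed, and the stated pair of figures belongs to none of these in particular.

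The end points also overlap and may not all apply to the same children. Section 2.3.4.2 calculates BMI from weight. Section 2.3.4.3 lists "HOMA-IR (Type II diabetes) and c-peptide (Type I diabetes"), while section 2.3.1 enrols children with obesity or with either type of diabetes. If the label restricts HOMA-IR to Type II diabetes, 40 per group is not its sample size.

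Phase II is the randomised test of the personalised algorithm against usual care. If the two sections are not reconciled before the data are seen, a reader of the results cannot tell which comparison the trial was designed to answer.

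**Working it through.** **Inputs.** Difference 15, SD 20, 40 per group, two-sided 5% (section 2.3.5.1). Number of primary end points m = 6, or 4 on the narrower reading (section 2.3.6). The documents give no correlations between end points, so a common correlation from 0 to 0.9 is assumed.

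**1. The plan's own figure.** Standardised difference d = 15/20 = 0.75. Noncentrality = d × √(n/2) = 0.75 × √20 = 3.354. Normal approximation: power = Φ(3.354 − 1.960) = 91.8%. Noncentral t with 78 degrees of freedom: 91.2%. The stated figure of at least 90% reproduces for one endpoint.

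**2. Success on any one, each tested at 5%.** With independent tests the chance of at least one false positive is 1 − 0.95^m:
- m = 6: 1 − 0.95⁶ = 26.5%
- m = 4: 1 − 0.95⁴ = 18.5%

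Simulation of equally correlated test statistics (200,000 draws per setting) gives:

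| Assumed correlation | Six | Four |
|---|---|---|
| 0.3 | 24.0% | 17.4% |
| 0.5 | 20.7% | 15.5% |
| 0.7 | 16.3% | 13.0% |
| 0.9 | 10.7% | 9.4% |

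Power per endpoint stays at about 91% under this rule.

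**3. 5% split by Bonferroni.** Same noncentral t calculation at 0.75 SD:
- m = 6, level 0.05/6 = 0.0083: power per endpoint 73.9%. Restoring 90% needs 57 per group (114 children).
- m = 4, level 0.05/4 = 0.0125: power per endpoint 78.5%. Restoring 90% needs 53 per group (106 children).

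**4. All six must succeed, each at 5%.** A false overall success has probability at most 5%. With a true 0.75 SD on every endpoint, power for independent tests is 0.912⁶ ≈ 58% (0.918⁶ ≈ 60% with the normal figure). In simulation it rises to 85% at correlation 0.9.

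**Side by side.** Step 2 keeps the power and loses the 5%. Steps 3 and 4 keep the 5% and lose the 90%. Only a single endpoint, as in step 1, gives both figures as section 2.3.5.1 states them.

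**The case against.** **The analysis plan may set the rule.** Section 2.3.6 does not say that each endpoint is tested at 5%; for Study I that level appears only in the sample-size paragraph. A multiplicity method is commonly left to the statistical analysis plan, which is not shown, and outcomes are also described in Deliverable 2.8. This stands, so the absence of a correction is not the point here. The point is that two sections of this protocol disagree on how many primary end points there are. An analysis plan that picked one would contradict section 2.3.6.

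**Some rules could meet both figures.** A fixed testing order would keep 5% and 91% for the first endpoint, but no order is stated. With Bonferroni over six and success on any one, the chance of at least one success is about 87% (correlation 0.9) to almost 100% (independence). That needs a true 0.75 SD effect on all six, whereas the sizing assumes it for one.

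**Power depends on the analysis.** The figures use the two-sample comparison of section 2.3.5.1, whereas section 2.3.6 plans repeated measures. Suppose 0.75 SD refers to the raw SD and the test is on change from baseline. The effect then becomes 0.75/√(2(1 − r)), and Bonferroni power over six is 55%, 74% and 94% at assumed baseline-to-end correlations r of 0.3, 0.5 and 0.7. So the loss of power is conditional.

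**Tempting stronger readings.** A reader might infer that both the 5% and the 90% fail together. They do not: no rule in steps 2 to 4 breaks both. A reader might also infer that any one significant marker would count as validation of the platform. The protocol states no such rule; section 2.4 describes validation as showing how the framework carries over to clinical practice and mentions no test.

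**Conclusion.** The contradiction between sections 2.3.5.1 and 2.3.6 is real and is wrong as written. The 90% power is correct for one endpoint at 5%. It cannot stand beside a 5% overall error rate for an unordered list of six, or of four, primary end points.

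The size depends on a decision rule that the protocol does not give. Success on any one at 5% each would put the overall false-positive rate at about 11% to 26% for six, or 9% to 19% for four. The upper ends assume independence, and the overlap among the end points makes a lower figure more likely. A Bonferroni split would leave about 74% (six) or 78% (four) power per endpoint, in a two-sample comparison at 0.75 SD. Requiring all six would leave about 58% to 85%. The correlations of 0 to 0.9 are assumed throughout.

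**What to change.** Before Phase II randomisation, name one primary endpoint, in the same words, in sections 2.3.5.1 and 2.3.6. State that the difference of 15 and SD of 20 belong to it, with the unit. List the other end points as secondary, and mark the same choice in section 2.3.4.3. The power then stays at 91.2% with 80 children and the cost is wording only. What the sponsor gives up is claiming success on whichever marker moves.

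If several must stay primary, say whether the list is six or four, state the decision rule (for example Holm or a fixed order), and restate the power at the adjusted level. This route may need more children: under Bonferroni with 0.75 SD and a two-sample comparison, 90% per endpoint takes 114 in total for six or 106 for four.

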2.3.5.2. Randomisation

The randomisation, either to Group A or Group B, will be performed by an 2X2 block randomization on the basis of age of children (i.e., ≤12 and >12 years old, 1:1 ratio) and sex of children (1:1 ratio). The random allocation sequence (i.e., sequentially numbered containers), will be developed using STATA v15.0 software and relevant commands. Specifically, stream random-number generators will be used. One seed value will set and then using the software and particularly a stream version of the 64-bit Mersenne Twister, Stata's default pseudorandom-number generator, a random sequence of binary numbers will be created that allocate children to each study's Group.

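### Phase II is compared by a two-time-point RMANOVA with the tested term unnamed and covariates taken from baseline tests; a pre-specified ANCOVA is never less efficient and uses data already collected

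*Protocol*

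**What the plan says.** All references are to Study I of the protocol.

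- **Method (2.3.6).** Groups A and B are compared on weight, BMI, blood glucose, insulin, A1C and HOMA-IR, all labelled primary, "using Repeated Measures Analysis of Variance (RMANOVA". The section does not say which RMANOVA term answers the question.
- **Adjustment (2.3.6).** Baseline values are first compared by t-test or Mann-Whitney test. Then: "All necessary adjustments (based on the baseline analyses) will be performed to ensure the robustness of the results". No covariate is named.
- **Schedule (2.3.1 and 2.3.4.2).** Biomarkers, clinical data and anthropometry are evaluated at the beginning and end of the six-month intervention. Section 2.3.4.1 adds monthly visits in both groups and speaks of evaluations at the Group A visits, which feed the next diet plan. No monthly outcome analysis is described.
- **Randomisation (2.3.5.2).** It is a "block randomization on the basis of age of children" (up to 12, over 12) and sex. Section 2.3.6 names neither as a model term.
- **Sample size (2.3.5.1).** "the required sample will be 80 children (40 per Group A or B"), for "statistical power of at least 90% at 5% significance level of two-sided hypotheses" and "0.75 standard deviations (SD) mean differences in the primary endpoint of the Study". The command shown is "power two means 100, diff (15) sd (20) n (80").
- **Scale of weight and BMI.** Section 2.3.4.2 gives BMI in kg/m². The growth paragraph of 2.3.4.3 says weight, height and BMI status "will be compared to the available growth charts proposed by the World Health Organization". Section 2.3.6 does not say which scale is analysed.
- **Regressions (first paragraph of 2.3.6).** Weight and BMI are among the dependent variables. The listed predictors include neither age nor sex.

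**The concern.** With one value before and one after treatment, RMANOVA makes poor use of the baseline: the group-by-time test subtracts it in full instead of weighting it by how well it predicts the end value. The group main effect is worse, because it averages a pre-treatment value, where no effect can exist, with the end value.

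The adjustment rule adds a second problem. In a randomised comparison any baseline difference is due to chance, so covariates chosen from baseline tests let chance decide the model. Covariates worth having are those that predict the outcome, and these can be named now: the baseline value and the two randomisation factors.

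Finally, the participants are 8 to 18 years old and growing. Weight and BMI depend on age and sex, so the scale of BMI needs to be fixed, and regressions of weight or BMI that omit age and sex are open to confounding. What is at stake is precision and pre-specification in the project's only randomised comparison.

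**Working it through.** **1. The plan's own figure.** Difference 15, SD 20, so d = 15/20 = 0.75, with 40 per arm and two-sided 5%. Noncentrality = 0.75 × √(40/2) = 3.354. Noncentral t with 78 df gives 91.2%; the normal approximation gives 91.8%. The claim of at least 90% reproduces for a plain comparison of two means.

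**2. Three analyses of the same data.** Let ρ be the correlation between baseline and end value. The documents give no ρ, so it is an assumption and is varied. SDs are taken as equal at both times, 0.75 is in units of that SD, and 40 children per arm are evaluable (2.3.5.1 gives no dropout figure). Variances are per child, in units of SD².

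- Group-by-time (change score): variance 2(1−ρ), effective d = 0.75/√(2(1−ρ)).
- ANCOVA on baseline: variance 1−ρ², effective d = 0.75/√(1−ρ²).
- Group main effect: estimates half the difference, variance (1+ρ)/2, effective d = 0.375/√((1+ρ)/2).

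Change-score variance divided by ANCOVA variance is 2(1−ρ)/(1−ρ²) = 2/(1+ρ), which is above 1 for every ρ below 1.

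Example at ρ = 0.3: change 0.75/√1.4 = 0.634; ANCOVA 0.75/√0.91 = 0.786; main effect 0.375/√0.65 = 0.465.

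| ρ (assumed) | Variance ratio 2/(1+ρ) | Power, group-by-time | Power, ANCOVA | Power, group main effect |
|---|---|---|---|---|
| 0.3 | 1.54 | 80.0% | 93.5% | 53.8% |
| 0.5 | 1.33 | 91.2% | 96.9% | 48.1% |
| 0.7 | 1.18 | 99.0% | 99.6% | 43.5% |
| 0.8 | 1.11 | 99.95% | 99.98% | 41.5% |
| 0.9 | 1.05 | about 100% | about 100% | 39.7% |

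On this reading of the SD, the group-by-time test keeps 90% power once ρ is about 0.48 or more. Children per arm needed for 90% (normal approximation), group-by-time against ANCOVA: 53 against 34 at ρ = 0.3, 38 against 29 at 0.5, 23 against 20 at 0.7, 8 against 8 at 0.9.

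**3. A smaller effect.** At 0.3 SD (assumed), where power is not near its ceiling, group-by-time against ANCOVA gives 26% against 33% at ρ = 0.5, 40% against 46% at 0.7, and 84% against 86% at 0.9.

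**4. Covariates chosen from baseline tests.** If six baseline tests were independent, the chance of at least one p < 0.05 under sound randomisation would be 1 − 0.95⁶ = 26%. The protocol states no threshold, so one version of its rule was simulated: adjust for the baseline value only when its baseline test has p < 0.05, otherwise analyse change. Type I error was 3.9% to 5.2% for ρ from 0.3 to 0.9, so it was not inflated. Power at 0.75 SD was 82% against 93% for pre-specified ANCOVA at ρ = 0.3, and 93% against 97% at 0.5.

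**5. Randomisation factors.** The further gain from age stratum and sex cannot be computed, because the documents do not say how much outcome variance they explain.

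**The case against.** The strongest reply is that RMANOVA is a valid method in a randomised trial and that the power loss hangs on a correlation the documents do not give. If weight and BMI track at 0.9 or above over six months, nothing is lost on them at the design effect. This stands: the gain matters only for end points with a lower correlation.

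A reader might infer that the stated 90% is wrong. It is not shown to be. The figure reproduces, and 2.3.5.1 does not say whether the SD is that of a level or of a change. If it is of change, the group-by-time test is the comparison that was sized and has 91.2% power at any correlation. The mean of 100 in the command leans towards a level but does not settle it. The variance ratio in favour of ANCOVA holds on either reading.

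A reader might also take power near 48% as the plan's own. The protocol never commits to the group main effect, and 2.3.4.3 speaks of changes, which points to group-by-time. The defensible criticism is that the term is unnamed.

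Nor do the documents say that weight and BMI are analysed raw. The only formula is kg/m², but 2.3.4.3 cites growth charts, so the scale is unspecified. Four of the six primary end points are unaffected by this.

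The monthly visits in 2.3.4.1 are a fair caveat. If outcomes were recorded monthly and entered in the RMANOVA, the equivalence with a change score would fail; no such analysis is described. Lastly, stable age and sex differences cancel in a change score, so omitting these factors costs precision there only if they predict change. The adjustment sentence also does not exclude them; it simply names nothing.

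**Conclusion.** The point holds as one of efficiency and pre-specification, not of bias, false-positive inflation or a wrong sample size. The protocol itself fixes RMANOVA and ties adjustment to the baseline analyses, so this is not merely detail left for a later plan.

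On the two-point schedule, and with equal SDs, ANCOVA is never less efficient than the group-by-time test. The gain at the design effect is 13.5 percentage points of power at a correlation of 0.3 (93.5 − 80.0), 5.7 at 0.5 (96.9 − 91.2), 0.6 at 0.7 (99.6 − 99.0), and negligible at 0.9. If the unnamed term were read as the group main effect, the effect would be halved and power would be about 40% to 54% for correlations from 0.9 down to 0.3. Naming the model removes that ambiguity. These figures assume 40 evaluable children per arm and 0.75 SD of the level.

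Selecting covariates by baseline tests makes the model depend on chance and, in the version simulated, loses power relative to ANCOVA fixed in advance. The missing age and sex terms in the regressions of weight and BMI are a separate, simple gap.

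**What to change.** In 2.3.6:

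- For each of the six primary end points, replace RMANOVA by ANCOVA of the end-of-intervention value on group, baseline value, age stratum (up to 12, over 12) and sex, fixed in advance. Report the group coefficient with its confidence interval.
- Remove baseline significance tests as the basis for adjustment. A descriptive baseline table is enough.
- State the scale on which BMI is analysed. As 2.3.4.3 already refers to WHO charts, BMI-for-age z-score can serve for the BMI end point. Weight stays as a primary end point.
- State that the outcome values are those at the start and end, and say whether any monthly measurement under 2.3.4.1 enters the outcome analysis.
- Add age and sex to the linear regressions of weight and BMI.

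The cost is a rewrite of the analysis section. Baseline values, age, sex, weight and height are already collected, and no extra visit, measurement or child is needed. The choice of BMI scale defines an end point as well as its wording, so it should be settled before Phase II outcomes are seen.

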2.3.1. Study design

The details of the study design where optimized following discussions with the NUTRISHIELD partners (during the meeting held on Athens 9-10/4/2019, mails exchange and teleconferences) to better serve the project purposes. Small deviations from the Description of Action were decided regarding the study design related to the groups and the timeline without altering the overall goals of the study.

The proposed study is a two-arm, parallel, randomized controlled study, with a dietary intervention for children (8-18 year old) with obesity or diabetes (type I or II). It will be carried out in Ospedale San Raffaele hospital between M19 to M41. The study protocol will be approved by the Ethics Committee, and written informed consent will be obtained from all caregivers and/or participants. All procedures regarding volunteers' recruitment and participation, data security and handling will be in absolute accordance with the principles set under Work Package (WP) 9, concerning Ethical Requirements, and more specifically stated on Tasks 7.1 and 7.2 and D 7.2.

H2020 Contract No 818110

The study will be divided into two phases:

- 1. **Phase I**: the **Observational** phase, lasting at least four months. During this period children will be recruited and their diet and biomarkers will be assessed once, as described below. At the end of the observational phase and recruitment period, the study will pause for nine months (from M23 to M31) in order to perform machine learning analyses, feed the platform and train the personalized nutritional algorithm with the results from the preceding assessments of the observational phase.
- 2. **Phase II**: the **Intervention** phase, lasting six months. During this period children recruited in the study will be randomly allocated to one of the two groups:
 - Group A (Intervention) will receive a NUTRISHIELD-derived personalized diet
 - **Group B (Control)** will follow the standard European dietary guidelines for obesity/diabetes, i.e. the usual care/control diet.

Diet as well as biomarkers and clinical data will be evaluated at the beginning and at the end of the intervention phase.

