4.3.5. Statistical analysis

Association of acquired measures with dietary measures will be explored. Additionally, the relationship in between acquired measures, other than dietary intake, will be studied. Categorical values will be explored with Chi-square analysis. Student's t-test will be employed to test associations of continuous, independent variables. Correlations between continuous variables will be tested with Spearman's r coefficient. A p-value of 0.05 is considered significant.

Statistical analyses will be performed with the use of STATA statistical software (STATA Corp LLL, College Station, TX, USA).

Finally, additional statistical analysis with the view of deriving additional insights and influences in personalised nutrition will be presented in D2.5.

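### Study I assigns RMANOVA, a single-outcome method, to the multivariate microbiome profile, with no global test; on raw relative abundances, taxon by taxon, it can flag taxa that did not change

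*Protocol*

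**What the plan says.** Protocol section 2.3.6 (Study I) names repeated measures analysis of variance for the Phase II comparison of weight, BMI and glycaemic markers. It then extends that method to lipids, dietary intake, urine biomarkers and, at the end of the list, "biomarkers of intestinal inflammation and microbiome profile, using the aforementioned method". Section 2.3.4.3 treats the microbiome as an outcome of the intervention: "changes in the gut microbiome related to dietary modifications are expected to occur". It names no taxonomic level, scale or summary measure.

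On timing, section 2.3.1 states: "Diet as well as biomarkers and clinical data will be evaluated at the beginning and at the end of the intervention phase". Section 2.3.5.1 plans 80 children, 40 per group, for "statistical power of at least 90% at 5% significance level of two-sided hypotheses", based on a difference of 15 with SD 20.

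Section 2.3.6 also promises adjustments, but these rest on the baseline analyses and are not a data transformation. Further statistical work is deferred to D2.5, where it is described as additional. Faecal sampling is referred to Deliverable 2.1.

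**The concern.** RMANOVA can be applied to a profile in only two ways: test its components one at a time, or reduce it to a summary that the protocol does not name. The first invites two errors.

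One is multiplicity: many taxa, each tested at 5%, with no control stated. The other is closure. Relative abundances sum to one, so when one taxon grows, the shares of all the others fall. The fall in share is real. What is spurious is reading it as a response of those taxa to the diet.

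Both bear on a secondary claim that the personalised diet alters the gut microbiome, in the phase that section 2.4 presents as the clinical validation of the project. With the measure unnamed, the choice could also be made after the data are seen.

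**Working it through.** **The plan's own figure.** The standardised difference is 15/20 = 0.75. Power ≈ Φ(0.75·√(40/2) − 1.960) = Φ(3.354 − 1.960) = Φ(1.394) = 91.8%; the noncentral t gives 91.2%. For 90% power, n per arm = 2·(1.960 + 1.282)²/0.75² = 37.4, so 38. The stated power of at least 90% with 40 per group is reproduced. Nothing below disputes it.

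**Form of the test.** With two time points, the RMANOVA group-by-time test equals a t-test on change. Two points are taken from section 2.3.1. Section 2.3.4.2 also speaks of repeated faecal sampling but gives no number.

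**Closure.** If a taxon with share s changes f-fold in absolute amount and nothing else changes, every other relative abundance is multiplied by 1/(1 + s(f − 1)):

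- s = 1%, f = 2: 1/1.01 = 0.99
- s = 5%, f = 2: 1/1.05 = 0.95
- s = 20%, f = 2: 1/1.20 = 0.83
- s = 40%, f = 2: 1/1.40 = 0.71
- s = 40%, f = 3: 1/1.80 = 0.56

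**Size at 40 per arm.** The simulations change one taxon in Group A only and count the unchanged taxa with p<0.05. The number of taxa (20 or 50), shares, fold changes and log-scale SDs (between child / within child) are assumptions. CLR is the centred log-ratio; a dash means no figure was computed.

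| Log SDs | Share of changed taxon | Change | Raw relative abundance | CLR |
|---|---|---|---|---|
| 0.7 / 0.4 | 20–40% | none | about 5% | – |
| 0.7 / 0.4 | 20–40% | ×2 | 14–31% | 5–6% |
| 0.7 / 0.4 | 20–40% | ×3 | 33–65% | 5–8% |
| 0.7 / 0.4 | 5% | ×2 | about 5–6% | – |
| 1.0 / 0.7 | 1–40% | none | 3.8–4.2% | 4.8–5.2% |
| 1.0 / 0.7 | 1–40% | ×2 | 4.4–7.5% | 4.9–5.4% |
| 1.0 / 0.7 | 20–40% | ×3 | 8.3–16.0% | – |
| 0.7 / 0.3 | 5–40% | ×2 | 6.2–46.4% | 4.9–5.3% |
| 0.7 / 0.3 | 5–40% | ×4 | 18.5–94.2% | 5.8–6.0% |

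The excess is large only when the changed taxon is abundant and its change is large relative to within-child noise.

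**Multiplicity alone.** For independent tests with no true change, the chance of at least one p<0.05 is 1 − 0.95^19 = 62% with 19 taxa and 1 − 0.95^49 = 92% with 49. The simulations gave 58–65% and 88–89%.

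**Limits of the log-ratio remedy.** If m of K taxa change f-fold, CLR multiplies every unchanged taxon by f^(−m/K). One of 50 doubled: 2^(−0.02) = 0.99. Ten of 50 doubled: 2^(−0.20) = 0.87, against 1/1.10 = 0.91 on relative abundance if those ten jointly hold 10%. Simulated with SDs 0.7 / 0.4, that case flagged 19.4% of unchanged taxa under CLR and 9.2% on raw relative abundance. With 15 of 50 taxa jointly holding 30% doubled, the figures were 37.5% and 33.2%.

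**The case against.** The strongest reply is that the harmful analysis is not in the document. The protocol says neither that relative abundances will be analysed nor that taxa will be tested one by one. RMANOVA on a diversity index would have no closure problem. Transformation, zero handling and false-discovery control are ordinary content of a statistical analysis plan, and one may exist. This stands against any categorical claim, and the missing detail is not itself the finding. It does not remove the point, because the protocol does not stay silent: it assigns a named single-outcome method to a multivariate outcome.

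Three stronger readings are tempting and not supported:

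- A reader might infer that a change in one taxon will be reported as diet effects on many others. The table shows rates from nominal upwards, all resting on assumed inputs.
- A reader might extend the point to Study III, where section 4.3.5 says that "the relationship in between acquired measures, other than dietary intake, will be studied". That section names no taxa, and section 4.4 describes linking measures collected outside the project with those studied in it. Nothing there commits the study to correlating taxa with one another.
- A reader might infer that spurious taxa would be fed to the platform. Section 2.3.1 trains the algorithm during the pause, on Phase I results. The protocol says in general terms that study findings feed the platform, but not that Phase II taxon-level tests do.

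It is also fair to object that the centred log-ratio is no guaranteed cure; the multi-taxon cases show this. That qualifies the remedy but leaves intact the need for a single global test and multiplicity control.

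**Conclusion.** The point holds in conditional form. RMANOVA is the wrong kind of method for a microbiome profile, and the plan gives no single answer to whether the profile differs between arms. Spurious taxon-level differences from closure arise if untransformed relative abundances are tested singly and an abundant taxon changes substantially. At SDs of 0.7 / 0.4 the false-flag rate runs from about 5% (5% taxon, doubling) to about 30% (40% taxon, doubling) or 65% (40% taxon, tripling). Noisier data bring a doubling back close to nominal, and quieter data push the rates higher. The multiplicity problem does not depend on closure: with 20 to 50 taxa and no effect, most trials would flag something.

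This is a secondary analysis worth correcting before data are analysed. The primary end points and the sample size do not depend on it.

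**What to change.** In section 2.3.6, take the microbiome profile out of the RMANOVA list and state:

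1. One prespecified global permutation test of the between-arm difference in change, for example PERMANOVA on Aitchison distance.
2. Taxon-level models on log-ratio values under false-discovery control, labelled exploratory, with a stated zero-replacement rule.
3. A sensitivity analysis with another log-ratio reference, because the centred log-ratio can itself flag unchanged taxa when many taxa shift.
4. If wanted, RMANOVA for a named scalar summary such as a diversity index.

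The cost is wording and standard software; no extra children, samples or visits are needed. The downside is small: taxon effects are read relative to a reference rather than as shares.
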